## **Inclusion and Exclusion Criteria:**

### **Inclusion**

- informed consent has been discussed with subject, subject has been given opportunity to ask questions, and has signed a current version of the consent and HIPAA documents prior to initiation of study procedures
- age 18-65 years including males, females and minorities and able to comprehend English
- diagnosis of DSM-V major depression and currently off antidepressant medication, unless otherwise approved by the PI or PI's designee
- Depression as the primary axis I disorder
- negative pregnancy test for women of childbearing potential
- not breast feeding
- two (or more) CRP tests conducted to establish reliability

### **Exclusion:**

- evidence of untreated or poorly controlled endocrine, cardiovascular, pulmonary, hematological, renal, or neurological disease
- history of CNS trauma or active seizure disorder requiring medication unless otherwise approved by principal investigator, or PI's designee
- current or history of migraines (>6 debilitating migraines per month), glaucoma, melanoma, or bleeding disorder of any kind
- autoimmune or inflammatory disorder of any kind
- embedded metallic objects, prosthetics made of paramagnetic metals, aneurysmal clips and/or a history of claustrophobia
- chronic infection (e.g. hepatitis B or C or HIV)
- chronic use of agents known to affect the immune system including glucocorticoid therapy within the past 6 months, methotrexate within the past 1 year, chemotherapy of any kind (past or present), immunotherapy of any kind (past or present), aspirin or non-steroidal anti-inflammatory drugs (NSAIDs) (within the past 2 weeks), statins (within the past 1 month), vaccinations (within the past 2 weeks), topical steroids (within the past 2 weeks), and antibiotics (within the past two weeks) unless otherwise approved by principal investigator or PI's designee.
- suicide attempt within six months of screening, or active suicidal intent or plan, or score >2 on HDRS or QIDS/PHQ-9 Suicide Item, unless otherwise approved by the PI or PI's designee
- a positive pregnancy test
- organ transplants
- current or history of cancer within the past five years besides basal cell carcinoma, unless otherwise approved by the PI or PI's designee
- a score of <28 on the Mini Mental Status Exam (MMSE), unless otherwise approved by the PI or PI's designee
- WRAT-3 score indicating less than 8th grade reading level, unless otherwise approved by the PI or PI's designee
- Either QIDS <14 or PHQ-9 <15, or HDRS <18, unless otherwise approved by the principal investigator or PI's designee
- history of the following: schizophrenia, schizoaffective disorder, other (non mood disorder) psychosis, depression secondary to a medical condition, mental retardation, dementia, or delirium
- Substance dependence [or abuse within the past year (except nicotine)], unless otherwise approved by the PI or PI's designee
- BMI >40 to limit the impact of morbid obesity on the results, unless otherwise approved by the principal investigator or PI's designee
- antisocial personality disorder diagnosis as assessed during clinical interview, as well as a history of hospitalization and/or recurrent suicidal behavior judged to be directly due to the personality disorder
- Current eating disorder (aside from binge eating related to depression), unless otherwise approved by the principle investigator or PI's designee
- Current OCD, exclusionary only if impacting daily functioning, as assessed by clinical interview
- any other condition which in the opinion of the investigator would make the patient unsuitable for enrollment, or could interfere with participating in or completing the protocol
- smoking more than one half pack per day, or e-cigarette equivalent, unless otherwise approved by the PI or PI's designee

- initiation of any of the following medications, unless otherwise approved by the PI or PI's designee: Aspirin or Aspirin-like compounds (single dose within 48 hours), Ibuprofen or Naproxen Sodium (single dose within 48 hours), Cholesterol medications, Antibiotics, Herbal Medications, Psychiatric or Psychotropic Medications (including sedative hypnotics, anxiolytic medications or pain medications), Omega-3 supplements, Topical Steroids, Vaccinations (within the last 2 weeks)
- Currently on antidepressant medication, unless otherwise approved by the PI or PI's designee

**Urine drug screening:** A urine drug test (DrugCheck: NxScan Onsite Testcup or equivalent as approved by PI or designee) will be performed for every patient at screening and prior to each MRI scan. The urine test will allow for the qualitative detection of drug or drug metabolites in urine, including benzodiazepines, methamphetamine, cocaine, THC and morphine. Identification of a urine test positive for substance use will exclude the subject from participation, unless substance is a prescribed medication, or otherwise approved by PI or study physician.

**Urine Pregnancy Test:** A urine pregnancy test may be performed for women of childbearing potential if it has been >30 days since their last screening labwork (which includes a quantitative, serum hCG test). Identification of a positive urine pregnancy test will exclude the subject from participation.

**Gender and Minorities:** Based on the composition of the patients treated for major depression at the Emory Clinic, Grady Health System, VAMC and community psychiatry clinics, we anticipate that an equal number of men and women will be included in the study. As for the racial composition of the sample, we anticipate 30-40% African Americans, 5-10% Latinos and 2-5% Asians, which is reflective of the community (city of Atlanta) from which our sample will be drawn.

**Dropouts:** Because participation in this study involves two screening visits followed within approximately 2 weeks by three study visits, we anticipate that there will be few subjects who will drop out between screening and the study visits. In our experience, however, there will be subjects who will have to be removed from the study because of a positive urine toxicology screen. In addition, some subjects may become too severely depressed and/or suicidal between enrollment and completion of the study. Given a conservative estimate of a 20% screen failures and 20% dropout rate, we will need to recruit ~ 225 subjects to reach the target of 80 subjects for analysis. Psychiatric staff is available throughout each subject's participation, and can provide on-site emergency care in the event of crisis.

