#### **Structured Clinical Interview for DSM-VIV (SCID-Modified):**

**Mood modules-** These modules from the SCID will allow for a categorical diagnosis of the presence or absence of major depression or other DSM-VIV mood disorder. Such categorical diagnoses will complement symptom severity ratings offered by the HDRS.

**Alcohol and Drug Abuse/Dependence Module:** These SCID sections allow for assessment for current or past presence of alcohol and drug abuse/dependence.

**Eating Disorder and Anxiety modules:** These sections allow for a diagnosis of the presence or absence of eating disorders and anxiety disorders.

**Psychotic module:** This module from the SCID will allow for the assessment of the presence or absence of psychotic symptoms.

**Salpetriere Retardation Rating Scale (SRRS):** The SRRS is a 15-item, clinician-administered scale to assess clinical psychomotor retardation (71). The 15 items of the scale are either related to motility or mental activity.

**Psychiatric History:** This form assesses the psychiatric history of the subject.

**WRAT-3:** The WRAT-3 is a very brief screening measure for reading level.

**Bipolarity Index:** The bipolarity index assesses five symptom dimensions that are characteristic of patients with bipolar disorder. The degree of severity of each dimension is calculated.

**Snaith-Hamilton Pleasure Scale (SHAPS-C):** Clinician administered assessment of anhedonia.

**Hamilton Anxiety Rating Scale (HAM-A):** The HAM-A is a 14-item clinician-administered scale that assesses the severity of symptoms of anxiety.

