in the current study to help reduce patient burden. Some labs or evaluations may be repeated at the discretion of the PI or PI's designee, if more current data is needed. We anticipate that at least 2 subjects per month (~24 subjects per year) will consent to enter this study. This estimate is based on ongoing projects that have been recruiting subjects for related studies over the past 5 years. Of subjects who meet entry criteria, our past experience suggests that approximately 20% will discontinue study participation.

Patients with MD enrolled in the study will meet DSM-V-TR criteria for a current major depressive episode without psychosis with a symptom severity score of  $\geq 18$  on the Hamilton Depression Rating Scale (HDRS) -17 item scale. To be included, subjects must not demonstrate active suicidal intent or plan and must score  $\leq 2$  on the HDRS or QIDS suicide item, and must have no suicide attempt within six months of screening. Enrolled subjects will have no history of the following: schizophrenia, schizoaffective disorder, other (non-mood disorder) psychosis, depression secondary to a medical condition, mental retardation, and substance dependence [or abuse within the past year (except nicotine)], dementia or MMSE  $<28$ , unless otherwise approved by the PI or PI's designee, or delirium. Subjects will be at risk for exclusion for a urine toxicology screen positive for ETOH or drugs of abuse. The presence of post-traumatic stress disorder, panic disorder, obsessive compulsive disorder or social phobia will not disqualify subjects from enrollment as long as depression is the primary diagnosis, though post-traumatic stress disorder may be considered as a covariate in statistical analyses. Enrolled subjects may have a comorbid personality disorder; however, subjects who meet criteria in clinical interview for antisocial personality disorder will be disqualified, as will subjects with a history of hospitalization and/or recurrent suicidal behavior judged to be directly due to the personality disorder.

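### The Section 5 exclusion list closes its suicide-risk bullet with an investigator waiver and does not name current psychotic depression; Section 6 sets both rules without a waiver

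*Combined protocol and SAP*

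**What the plan says.** **Suicide risk.** In Section 5, under Exclusion, one bullet covers three conditions: a suicide attempt within six months of screening, active intent or plan, and a suicide-item score above 2. Its later part reads "active suicidal intent or plan, or score >2 on HDRS or QIDS/PHQ-9 Suicide Item, unless otherwise approved by the PI", and it then extends the power of approval to a designee.

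Section 6 (Participant selection) covers the same ground: "To be included, subjects must not demonstrate active suicidal intent or plan and must score" 2 or less on the HDRS or QIDS "suicide item, and must have no suicide attempt within six months of screening". That sentence contains no waiver. The next one does, beside the MMSE limit: "unless otherwise approved by the PI or PI's designee, or delirium".

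**Psychosis.** Section 6 asks for a "current major depressive episode without psychosis with a symptom severity score of" at least 18 on the HDRS. Separately, it bars a history of "schizophrenia, schizoaffective disorder, other (non-mood disorder) psychosis". The Section 5 list carries only the second of these rules, as a history of "schizophrenia, schizoaffective disorder, other (non mood disorder) psychosis". Its diagnostic inclusion criterion asks for major depression and says nothing about psychotic features.

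**Which list staff use.** The Study Overview in Section 5 says eligibility is determined at the screening visits and points the reader to the Section 5 criteria.

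**The concern.** The two sections do not give the same answer for the same patient, and the conditions on which they differ are safety conditions. Under Section 5 as worded, the investigator or an unspecified designee could approve a patient with active suicidal intent, and a current psychotic depressive episode meets no named exclusion. Section 6 bars both patients.

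Section 9 says that patients with untreated major depression are followed for up to four weeks. It also requires that, if active suicidal ideation develops during the study, a board-certified psychiatrist is told at once and decides whether the patient may stay. An entry rule that lets a designee admit someone who already has intent or a plan is looser than the rule that applies once the patient is in the study.

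**Working it through.** No arithmetic applies. The check sets the two current texts side by side. Neither is an amendment log, and no redaction falls in the sentences compared.

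**1. Condition by condition**

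| Condition | Section 5 list | Section 6 |
|---|---|---|
| Active suicidal intent or plan | Excluded, in a bullet that closes with a waiver | Must be absent; no waiver |
| Suicide attempt within six months | Excluded, same bullet | Must be absent; no waiver |
| Suicide-item score above 2 | Excluded, same bullet; waiver applies | Must be 2 or less; no waiver |
| Current depressive episode with psychotic features | Not named | Barred |
| History of psychosis outside mood disorder | Excluded | Excluded |

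The sections agree on the last row and differ on the first four.

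**2. How far the Section 5 waiver reaches.** The bullet joins three alternatives with *or*, and the waiver follows at the end.
- Wide reading: it applies to all three alternatives. Nothing in the bullet limits it to the last, so this is the natural reading. Sections 5 and 6 then conflict on attempt, on intent or plan, and on item score.
- Narrow reading: it applies only to the item score. The sections then conflict on item score alone.

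There is a conflict on either reading. What changes is how serious it is.

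**3. Whether the missing waiver in Section 6 means anything.** Section 6 uses the waiver phrase one sentence later, for the MMSE limit. The phrase was therefore available when that paragraph was written, and it is not attached to the suicide conditions. This supports treating the difference as real.

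**4. Whether anything in Section 5 excludes psychotic depression.**
- The history bullet is limited to psychosis outside mood disorder, so psychosis within a depressive episode falls outside it.
- The SCID psychotic module allows "the assessment of the presence or absence of psychotic symptoms", but Section 5 attaches no eligibility rule to the result.
- The general bullet on conditions that make a patient unsuitable, in the investigator's opinion, allows refusal but does not require it.

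**5. Result for three example patients**

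| Patient | Section 5 alone | Section 6 |
|---|---|---|
| Active intent, waiver granted | Admissible on the wide reading; excluded on the narrow | Excluded |
| No intent, plan or recent attempt; item score above 2, waiver granted | Admissible on both readings | Excluded |
| Current psychotic depression, otherwise eligible | Not excluded by any named criterion | Excluded |

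Neither section says which one governs.

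**The case against.** **The sections can be read together.** A patient must satisfy the whole protocol, so Section 6 already bars everyone in question, and the psychosis point is an omission from one list. This largely stands for psychosis: nothing in Section 5 permits such a patient, and Section 6 is clear. It is weaker for suicide risk, because Section 5 grants a power of approval that Section 6 leaves no room for. In both cases the reader has to notice Section 6, while the Study Overview points to the Section 5 list.

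**The waiver may cover only the item score.** This is a possible reading, and the firm wording of Section 6 suggests that intent, plan and recent attempt were never meant to be waivable. It limits what can be claimed. It is also a reason to split the bullet, since doing so would only state what was intended.

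**There are many safeguards.** The protocol provides for the C-SSRS with referral, repeat interviews, on-site and on-call psychiatric cover, and DSMB review. A waiver permits approval without requiring it. All of this reduces the risk, but none of it settles who is eligible.

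**A stronger claim about the drug.** A reader might infer that L-DOPA itself makes these patients unsafe, because Section 10 mentions mental or mood changes. The documents do not support that as an argument here. The mention comes after, and apart from, the list of mild, transient effects that Section 10 links to acute dosing at the study doses, and each patient receives a single L-DOPA tablet.

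**Conclusion.** The inconsistency is real and should be corrected. The suicide-risk conditions are waivable in one section and not in the other. A current psychotic depressive episode is barred in one section and not named in the other.

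The difference in wording is certain. That the waiver reaches active intent, plan and recent attempt rests on the natural reading of the bullet. On the narrow reading, only the item-score rule conflicts. The practical consequence assumes that staff apply Section 5 without checking Section 6.

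Three further inferences go beyond the documents:
- That the protocol as a whole allows suicidal or psychotic patients to be enrolled. It does not, because Section 6 bars them.
- That such patients have been or will be admitted, or that the results would be biased or power lost. The documents give no figure for waivers or for psychotic features, so the number affected is unknown.
- That Section 6 excludes any past psychotic depression. Its rule concerns the current episode, and its history rule is limited to psychosis outside mood disorder.

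**What to change.** In the Section 5 exclusion list:
- Make an attempt in the six months before screening, or present active intent or plan, a bullet of its own with no waiver.
- Put the suicide-item score above 2 in a second bullet and give it one rule in both sections: either no waiver, as Section 6 now has it, or the same explicit waiver in each. Name the same scales in both; at present Section 5 includes the PHQ-9 item and Section 6 does not.
- Add a current major depressive episode with psychotic features, assessed by the SCID psychotic module.

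In Section 6, replace the restated criteria with a reference to the Section 5 list, so that only one text governs.

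The cost is a short protocol amendment. The SCID, HDRS and C-SSRS are already part of screening, so no assessment is added. A few patients who could enter under the present Section 5 wording may be refused.

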## 5. Study design and methods

Study Overview: Patients with major depression diagnosed based on DSM-V TR criteria between the ages of 18 and 65 (males, females and minorities) will be recruited to ensure a range of inflammation from low to high (as determined by plasma CRP). Research assessments will occur in the clinical research space of the Principal Investigator in the Emory Clinic Buildings and at the Emory University School of Medicine EUH CRN, a dedicated clinical research unit in the Emory University Hospital. Following a minimum of 2 screening visits to determine study eligibility (see inclusion and exclusion criteria below) and stability of plasma CRP concentrations (or at PI's, study physician or their designee's discretion), patients will undergo psychiatric assessments and ratings and will have a medical history and physical examination along with laboratory testing and research blood draw, and will undergo weight, height, waist circumference, body composition measurements, and a urine drug screen followed by behavioral testing. Patients may also be asked to undergo finger prick at screening or study visits to collect 20 ul of blood that will be used to rapidly measure CRP on a Diazyme hsCRP POC Test Kit (or equivalent as approved by PI or PI's designee) without patients having to undergo venipuncture. Patients may also be asked to have a lumbar puncture (LP) performed by an Emory Anesthesiologist on a separate visit between 7am-12 pm following hydration with 1 L of saline IV using standard sterile technique and local anesthesia with patients in the lateral decubitus position. Approximately 11 cc of CSF will be withdrawn. Upon completion of the LP, subjects will lie flat for approximately one hour and be subsequently discharged after ~4-6 hours from admission. Patients will participate in two additional outpatient study visits (see Table 1 for study protocol). The LP visit may occur approximately 1 week either before the first neuroimaging Study visit or one week after the last neuroimaging Study Visit, unless otherwise approved by the PI. After subjects have completed screening by meeting inclusion/exclusion criteria and moved into the L.P. and/or scanning visit phase of the study, an Abbreviated Clinical Interview and depression self-report (PHQ-9, see below) will be conducted if it has been more than 2 weeks since psychiatric assessments. Additional laboratory and medical assessments will be conducted if more than 4 weeks from screening, unless otherwise approved by the PI, study physician or PI's designee. This information will be used as study data and/or to improve patient safety by enabling monitoring of a subject's physical and psychiatric status during the study. Drastic fluctuations in psychiatric status (i.e. >25% change in depression scores) or medically significant changes in health status from H&P or labs will trigger a review by the Study Team (including the PI and/or study physicians) to evaluate appropriateness for continuation in the study and/or consider referral for further

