
treatment. Additional CRP testing, psychiatric assessments, or medical assessments may be conducted as indicated by the PI, study physician or PI's designee. Prior to each MRI neuroimaging session, patients will undergo a urine toxicology screening (Testcup for drugs of abuse, or equivalent as approved by PI or PI's designee) for safety and exclusion of substance abuse. On the last screening visit, patients will undergo blood sampling in the morning (collected at the same time as blood draw for safety labs and/or CRP), and complete neurocognitive testing. During Study Visits 1 & 2, subjects will complete a series of self-reports in the morning, have MRI scans (including resting-state fMRI and ASL) pre- and post-L-DOPA or placebo administration from about 9 AM to 12:30 PM, and undergo blood sampling and selected neurocognitive testing after the MRI scans from about 12:30 to 2 PM. L-DOPA or placebo, which will be administered double-blind (randomized by the Emory IDS), will be administered in the waiting area of the Neuroimaging Facilities. Patient's vital signs will be monitored by a Study Physician or designated Nurse Practitioner before, during, and after drug administration. At each study visit, 6 ml of research blood will be collected at 4 degree for extraction of plasma to measure inflammatory markers and/or L-DOPA concentrations. Two 3 ml samples will be collected (at the screening visit #2 only) for whole blood mRNA gene expression. 2 buffy coat samples from the first research blood collected for plasma (screening visit #2) will also be stored for genetic analyses of relevant gene polymorphisms and DNA methylation. In order to further assess immune cell profiles, we will also collect 10 ml of whole blood in EDTA at room temperature for immune cell extraction. Some samples may be sent to other labs for additional analysis. Safety laboratory tests will be conducted at screening, which will include a hematocrit (CBC with automated differential), electrolyte panel (comprehensive metabolic panel), urinalysis with microscopic, and serum quantitative pregnancy test (for women only). A CRP test will be completed at both screening visits to establish stability, and may be repeated during study visits at the PI's or PI's designee's discretion. Subjects who smoke cigarettes must refrain from smoking 30 minutes before all blood draws and 2 hours prior to mRNA sampling. Subjects who smoke half a pack per day, or e-cigarette equivalent, will be offered a nicotine patch during study visits to reduce the effects of withdrawal on fMRI scans.

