  - h) urinalysis with microscopic
  - i) serum quantitative pregnancy test (if female)
  - j) urine toxicology for drugs of abuse
  - k) Pt/INR (only done if S will be participating in the LP procedure)
  - l) PTT (only done if S will be participating in the LP procedure)

Procedures	Initial Visit	Screening #1†	Screening #2†	Lumbar Puncture Visit	Additional (If needed)	Study Visits #1-3
Consent/re-consent	X	[X]	[X]	[X]	[X]	[X]

Physical exam		X	[X]		[X]	[X]
Health update and vitals			[X]	[X]		[X]
Concomitant Medications		X	X	X	[X]	X
Adverse Events		X	X	X	[X]	X
History of Chronic Conditions		X			[X]	
CRP	[X]	X	[X]	[X]	[X]	[X]
Safety Labs #	[X]	X	[X]	[X]	[X]	[X]
Additional Safety Labs ##	[X]	[X]	[X]	[X]	[X]	[X]
Pt/INR, PTT (for LP only)	[X]	[X]	[X]	[X]	[X]	[X]
Research blood draws †		[X]	X	[X]	[X]	X
MRI Scan						X
Neurocognitive tests		[X]	X	[X]	[X]	
Neurocognitive tests *				[X]		X
Psychiatric Assessments Y	X	[X]	[X]	[X]	[X]	[X]
Psychiatric Assessments YY		X	[X]	[X]	[X]	
Psychiatric Assessments YY Y				[X]		X
Self Reports	X	[X]				
Self Reports *			X	[X]	[X]	
Self Reports **						X
MRI Scan Food, Drink and Cigarette Intake Form +						X
Lumbar Puncture				X		
Placement of ECG patches		[X]	[X]		[X]	

[X]: To be completed when indicated.

† Screening 1 & 2 can be completed on the same day if preferred by patient

#Safety Labs: Complete Metabolic Panel, CBC w diff, Serum Preg Test (females), Urinalysis w micro, Urine drug test

##Additional Safety Labs (screening #1 or screening #2): HIV Ag/Ab, Hep B Ag, Hep C Ab, ANA, TSH, Glycosylated Hemoglobin, EKG, Chem 7: electrolytes, urea, creatine, glucose, and/or hsCRP

Pt/INR, PTT to be completed for subjects who consent to LP within 2 weeks of procedure at any visit

‡ To be completed at one of the two screening visits during collection of safety labs and/or screening CRP

Neurocognitive tests: EEFRT, TMT-A, TMT-B, Digit Symbol Task, FTT, Reaction Time Task, Choice Reaction, Delayed Matching to Sample, Spatial Working Memory, RAVLT, Stroop word and color test to be completed at the end of the last screening visit

Neurocognitive tests\* (Visits 1 & 2): EEFRT, TMT-A, Digit Symbol Task, FTT, Reaction Time Task

Y Psychiatric Assessments (Initial Visit): PHQ-9 or QIDS

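### Pregnancy is a non-waivable exclusion, yet on the planned schedule no pregnancy test is required between screening and the two MRI/dosing visits

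*Combined protocol and SAP*

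**What the plan says.** **The criterion is firm.** The Inclusion list in Section 5 asks for a negative pregnancy test in women of childbearing potential, and the Exclusion list bars anyone with a positive one. Neither entry has the investigator-approval clause that many neighbouring criteria carry. Section 6 lists pregnancy among conditions that might confound the results or contraindicate MRI or L-DOPA. Section 7 (Interim Monitoring and Early Stopping) lists it as sufficient reason to discontinue.

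**The testing is firm only at screening.** The Study Overview in Section 5 places the serum test among the screening safety labs, and Section 7 also places pregnancy testing at screening. In the table of procedures, Safety Labs ("CBC w diff, Serum Preg Test (females), Urinalysis w micro, Urine drug test" among the contents) carry an unbracketed mark at Screening #1 only. At the study visits the mark is bracketed, which the key defines as "To be completed when indicated".

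**Two time-based rules govern later testing.** The Study Overview states: "Additional laboratory and medical assessments will be conducted if more than 4 weeks from screening, unless otherwise approved by the PI", with the study physician or a designee also able to approve otherwise. The Urine Pregnancy Test paragraph states: "A urine pregnancy test may be performed for women of childbearing potential if it has been >30 days since their last screening labwork". A positive result on that urine test excludes the woman.

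**Urine is collected before every scan.** The urine drug test "will be performed for every patient at screening and prior to each MRI scan", and the Study Overview says the same: "Prior to each MRI neuroimaging session, patients will undergo a urine toxicology screening".

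**The concern.** The plan states a strict criterion but does not check it when it matters, which is on the day of the scan and the dose. A negative result at screening says nothing about a conception after that date. A woman who conceives in the interval, or whose pregnancy was too recent to show at screening, can go through both MRI/dosing visits without any required test having been missed. In the crossover design one visit delivers L-DOPA and the other placebo. Whether the exclusion and the discontinuation rule work for an unrecognised pregnancy then depends on a member of staff choosing to test.

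**Working it through.** No sample-size, power or error-rate figure is involved. The check compares each retest trigger with the planned schedule.

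**Inputs**

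- Screening to study visits: Section 5, Dropouts, describes "two screening visits followed within approximately 2 weeks by three study visits", so about 2 × 7 = 14 days.
- Consent to final assessment: Section 9 gives a maximum of 4 weeks, so 4 × 7 = 28 days. Screening laboratory work done for this study follows consent, so it is at most 28 days old at the last visit.
- Trigger A, repeat laboratory work (Study Overview): more than 4 weeks, so more than 28 days; waivable.
- Trigger B, urine pregnancy test: more than 30 days; optional.
- MRI/dosing visits per patient: 2, of which 1 is L-DOPA (250 mg with 50 mg carbidopa).

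**Comparison**

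| Days since screening labwork | Trigger A (> 28) | Trigger B (> 30) | Pregnancy test required? |
|---|---|---|---|
| 14 (planned gap) | not reached | not reached | no |
| 28 (planned maximum) | 28 > 28 is false | 28 > 30 is false | no |
| 29 (1 day over) | reached, waivable | not reached | only if A is not waived and is read to include hCG |
| 31 (3 days over) | reached, waivable | reached, but optional | same; B adds no obligation |

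Required pregnancy tests between screening and dosing on the planned schedule: 0, across 2 MRI/dosing visits.

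**The two urine tests side by side.** The drug test and the pregnancy test are described in consecutive paragraphs of Section 5. The drug test is mandatory for every patient before each scan. The pregnancy test *may* be done, and only after the 30-day condition is met. Both the drug test and the serum pregnancy test sit in the Safety Labs row, with the same bracketed mark at study visits. The text overrides the bracket for the drug test; no text does so for pregnancy.

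**Off schedule.** Section 6 lets earlier screening assessments from related studies be reused, with repeats at the investigator's discretion. Reused laboratory work may pre-date consent to this study, so the 28-day limit need not apply to it. Trigger A could then require a repeat unless waived, while the urine test remains optional.

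**Load of a mandatory test.** With 80 patients analysed and 50% women (Section 6), 80 × 0.5 = 40 women and 40 × 2 = 80 urine tests at most among completers. The true number is lower, because some women aged 18 to 65 are not of childbearing potential; the documents do not give that share.

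**The case against.** The strongest reply has five parts.

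1. *A check already happens before every scan.* The MRI Neuroimaging paragraph requires a safety screening form before each session and withholds the scan from anyone with a contraindication. A known or suspected pregnancy could be caught there. This stands in part. The form's contents are not shown, however, and a questionnaire cannot detect a pregnancy the woman does not know about.

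2. *The bracketed mark proves little.* The mandatory drug test has the same mark, so the table alone does not show that a test is not required. This is fair. The point rests on the optional wording of the Urine Pregnancy Test paragraph; the table merely fails to supply an obligation.

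3. *The four-week rule probably includes hCG.* It does not name hCG, but the Urine Pregnancy Test paragraph says the screening labwork includes a serum hCG test, so this reading is natural. Granting it changes nothing on schedule: the rule begins after 28 days and can be waived.

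4. *The plan has simply chosen a validity window of about four weeks for a quantitative serum test.* That is a coherent choice, and the documents do not show it to be wrong. But even when the 30-day window lapses, the urine test stays optional. A window that obliges nothing when it closes does not enforce a non-waivable criterion.

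5. *Harm is not shown.* Section 9 says no high-risk procedures are involved, active exposure is a single dose, and Section 10 describes no fetal risk. This stands as a limit on how serious the point is. The plan itself nevertheless chose to exclude pregnant women without exception.

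The consent pages are not in the reviewed text and may contain advice on contraception or on reporting a pregnancy, so nothing is inferred from their absence.

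**Conclusion.** The concern holds. On the planned schedule of about 14 to 28 days, the plan requires no pregnancy test between screening and either MRI/dosing visit. The study team is free to test at those visits but is not obliged to. Potential active exposure per affected woman is one 250/50 mg dose, plus the MRI sessions at both visits. The number of women affected cannot be estimated from the documents.

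The conclusion assumes that the schedule in Dropouts and Section 9 is kept and that screening laboratory work is done within this study. If visits run late or earlier results are reused, a repeat may be required under the four-week rule unless it is waived.

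This is a matter of participant safety and of enforcing eligibility. It has no bearing on the endpoints, power or analysis. The change should be made because the gap is clear and closing it costs very little.

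**What to change.** Reword the Urine Pregnancy Test paragraph in Section 5 so that the test is mandatory and not tied to elapsed time, for example: *Women of childbearing potential will have a urine pregnancy test before each MRI/dosing visit, run on the sample taken for the drug screen; the result will be read before scanning starts and before study drug is given.* Keep the existing consequence of a positive result. In the table of procedures, add a separate row for this test with an unbracketed mark at the study visits.

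The cost is one strip and a few minutes per visit for each woman of childbearing potential, with no new specimen. A false positive would occasionally delay a visit until a serum test is back. Sample size, power and blinding are unchanged.
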